Males who present with exclusion criteria for one of the medical reasons listed above will be referred to the appropriate specialist for management of their conditions. Additionally, any men who have an anatomic contraindication but still want circumcision, can be referred to an urologist for further management. In keeping with standard national practice, clients presenting with specific disease conditions such as STIs or TB may be treated on-site or referred for care elsewhere if appropriate services are not available on site. Furthermore, males who are HIV+ will be assessed to determine if they are on antiretroviral therapy (ART). Those not on ART will be referred for ART.

Client Withdrawal Criteria

A client has the right to withdraw from the evaluation at any time, for any reason, without prejudice to his future medical care by the provider or the health facility (see Appendices V and VI for the client and minor client assent forms). If a client withdraws after consent, but prior to device placement, the client will be replaced until the desired sample size is reached and the data will be excluded from analysis. If a client withdraws after device placement, the client will not be replaced and the existing data will be included in the analysis, but no attempts will be made to collect further data other than that required for clinical documentation of the removal visit. The reason, timing and circumstances of the withdrawal will be documented and analyzed. The client will subsequently not be included among those selected for the day 28 in-person interview, nor will they be asked to return for the day 49 follow-up visit to assess healing. When the client withdraws, they will be informed that they may still return to the clinic for removal of the device as scheduled, and contact the clinic should they have further questions, suffer an AE, or experience other difficulties healing.

A client will be informed in advance that if he wishes to withdraw from the evaluation after ShangRing placement but before scheduled removal, he must still return to the provider for device removal on day 7 for his own health. The client will also be advised that once applied, it is not safe to remove the device before day 5. If the client requests removal on day 5 or 6, it will be removed as requested. The number and reasons for client withdrawals will be recorded and included in the final evaluation report (See Appendix XXII).

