Sites should provide a brief orientation to other health centers in the catchment area. The purpose of this orientation is to provide these health centers with an overview of the pilot, to offer the health centers guidance on how to provide care for any pilot clients that may present to their clinic, and to request the health centers alert the pilot sites in the event that a client from the pilot seeks follow-up care from the center (i.e. in the case of the AE), and provide the health centers with contact information for implementation pilot staff in order to do so.

Sample Size, Data Collection and Analysis Timeline

The total sample size for this implementation pilot is 575 male clients at the selected sites in Shinyanga, Tanzania. Both HIV- and HIV+ men will be included in the sample. The sample size of 575 males is consistent with the framework for circumcision device introduction as proposed by the WHO (see appendix I below). Additionally, this sample size is powered to detect the occurrence of adverse events, which is estimated to be 2%. A minimum of 335 males are necessary for 95% confidence that the population proportion is within $\pm 1.5\%$ with an observed adverse event rate of 2%. An additional 240 males will be recruited for further confidence in the results, and to align with the WHO framework. The evaluation teams will enroll males until the 575 sample size figure is achieved. All 575 males to be considered for the data analysis will be enrolled upon completion of the training phase.

All data collection will begin as soon as the first circumcision of an enrolled client occurs. Data will continue to be collected until the country has performed 575 circumcisions with the ShangRing device, and all post-circumcision follow-up data collected from clients as detailed in this protocol is complete. After the 575 circumcisions and all follow-up information is collected, the analysis of data as described per the primary and secondary endpoints will begin. If after the country has finished 575 circumcisions, and wishes to conduct the analysis necessary to inform national policy for the purposes of implementing the ShangRing device on a wider scale, that country may continue to enroll clients, and the first 1000 circumcisions performed should be monitored through active surveillance, as detailed in the WHO framework, and the country should perform its own data analysis as needed.³¹

Supplies and Logistics

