A physician will evaluate each AE for severity, seriousness, and relationship to the MC procedure, per the categories and criteria delineated in the *AE Action Guide for Voluntary Medical Male Circumcision by Surgery or Device, 2nd Edition* (see Appendix XV for table of AEs and severity). To ensure objectivity, the evaluating physician will be brought in from a site other than where the circumcision was performed. Any evaluating physician should be trained in male circumcision, and have experience evaluating adverse events. Methods to assess the severity, seriousness and relatedness of the AE are detailed in the evaluation SOP manual. Evaluation physicians will be trained to make these assessments in a manner as standardized as possible. The site coordinator will verify that this information will be captured during every evaluation subject visit. AEs will be managed medically as appropriate, and will be followed until resolution or until a clinically stable endpoint is achieved.

The incidence and severity of all AEs related to the circumcision procedure will be documented and collected on the appropriate visit section and device-related events form of the CRF. This form will include a description of the onset, duration, relationship to the procedure, severity, seriousness, and final outcome of the AE. Severe and serious AEs, as well as AEs related to client self-removal of the ShangRing, will also be documented on the ShangRing Device Related Adverse Events form (see Appendix XIV), which must be completed for all AEs that result in hospitalization and all AEs classified as severe per the AE classification guidelines, as well as for those whose severity cannot be classified. The evaluation will compile and analyze mild, moderate and severe AE to determine the AE rate. All other device-related events, including expected side effects and occurrences resulting from clients' failure to follow instructions, will be compiled and summarized to inform program policy related to ShangRing use.

For the purposes of this evaluation, **all** severe AEs must be reported to the CDC **within 24 hours of notification**. Standard reporting procedures for all **notifiable** AEs must be followed per PEPFAR and national guidelines.

ShangRing and Tetanus

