Baseline demographics and client characteristics will be presented in tabular format using descriptive statistics. Binary data such as adverse events will be presented as counts and percentages and the upper limit of the estimate of the AE rate (percent of clients with one or more AE) will be based on a two-sided 95% confidence interval. Adverse event rates will be compared descriptively with the reported rates of similar treatments reported in Tanzania and elsewhere, including: comparison against AE rates found in other studies of ShangRing, comparison against AE rates found in studies of other circumcision devices, and comparison against reported rates of AEs in studies of surgical circumcision. No formal hypothesis tests will be done comparing AE rates in this evaluation to other AE rates.

Adverse event rates will be presented by seriousness, severity, relation to device and outcome by site and by cadre. Continuous data will be represented by a mean, standard deviation, median, minimum and maximum together with 95% confidence intervals for the means. The number and percent of subjects who fail to complete the evaluation will be assessed. Time to withdrawal may also be assessed. The procedure time will be calculated. The first 15 procedures performed by each provider will be compared to the last 15 procedures by that provider with respect to procedure time, to evaluate whether procedure time is shortened with experience. All of the first and last 15 procedures evaluated will take place during the main implementation pilot phase. If a provider does not perform 30 total procedures following the training phase, then the first half of the total number of procedures performed will be compared against the last half. Adverse event rates from the training and post-training phases will also be reported, as well as an overall AE rate. Procedure times during the provider training phase will be tracked, but not used for comparisons. The differences in mean procedure times will be compared with a t-test or a non-parametric equivalent.

Standard statistical software packages R, Stata or SAS will be used for the analysis. No corrections for missing values will be imputed. The data will be analyzed and presented “as-is”.

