Participation in this evaluation is believed to pose no more than minimal risks. Potential complications of the ShangRing device circumcision include excessive bleeding, hematoma, infection, pain, wound dehiscence, injury to the glans or urethra, excessive or insufficient skin removal, and poor cosmetic results. The use of the ShangRing device has yielded low rates of adverse events in different studies. In a proof of concept evaluation in Kenya, all 40 procedures were completed successfully.³⁴ Only three mild adverse events, all cutaneous injuries of the skin of the penis, was reported among the 40 clients (7.5%) and mean pain scores were low. A second evaluation in Kenya enrolled 197 men, each of whom received successful ShangRing circumcisions, these were compared against 201 men who received conventional surgical circumcisions.³⁵ The ShangRing group experienced AEs at a similar rate to the conventional surgical circumcision group, with 14 moderate and one severe AE in the ShangRing group (7.6%) and 10 moderate AEs in the conventional surgical circumcision group (5.0%). The severe AE was a case of pain that occurred in the ShangRing group during the circumcision. The other AEs included: wound dehiscence, post-procedure pain, and an anesthetic complication. All AEs were

treated and resolved without problems. The pain scores between the two groups were similar at most points of time, with the exception that the pain during an erection while the device is in place was significantly higher for the ShangRing group. A comparative evaluation in Uganda found that a majority of men chose ShangRing over the dorsal slit method when asked to choose a preferred procedure, 508 chose ShangRing compared to 113 (though four men who chose ShangRing had to receive conventional circumcision when the ShangRing procedure failed, these failures occurred early in the evaluation and were attributed to provider inexperience).³⁶ There were no differences in the rate of moderate and severe AEs between the two groups – five total (1%) in the ShangRing group, and one (.9%) in the conventional surgical circumcision group. The AEs included post-operative pain, bleeding, infection, wound dehiscence, and insufficient skin removal. Additional studies in Kenya and Zambia have found similar rates of AEs between ShangRing procedures and conventional circumcision.³⁷

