Client is eligible for ShangRing circumcision (circle one)? Yes No If No, Specify Reason: _____

Confirmation of client's eligibility (circle one):

1. In good health: Yes No
2. Counseled: Yes No
3. Consented: Yes No N/A (13-17 years old)
4. If 13-17 year-old client, consent by parent/guardian and assent by client: Yes No N/A

If 'No' for any of the above, explain: _____

Part 2 – ShangRing Device Placement Procedure

Device size: _____ Expiration Date (dd-mm-yyyy): _____

If the device application is not the same day as the screening report, has there been a change in the genitals (compare to screening visit report)? Yes No

Time placement procedure began (e.g. 14:30): _____

Time placement procedure ended (e.g. 14:45): _____

Comments: _____

Was the device applied according to its Instructions for Use (circle one)? Yes No

If "No," explain in detail: _____

Was the penis disinfected before applying the device (circle one): Yes No

What form of anesthesia was used? Indicate injection/cream, what kind for each, and for injection provide dosage: _____

Please Attach ShangRing Label Here:

Was there an Adverse Event during placement (circle one)? Yes No

If yes, how would you rate the AE (circle one, refer to definitions below): Mild Moderate Severe

Severity cannot be classified (if problem with placement or device malfunction)

Adverse Event Definitions:

Mild: classification indicates minimal or no intervention is required beyond reassurance and observation

Moderate: classification relates to those AEs that are neither mild nor severe, require intervention, and are usually managed on site

Severe: classification requires extensive intervention with referral or specialist input

NB: If any Moderate, Severe, or Severity not classified adverse events above are checked, complete the AE form.

Full name and surname of clinician placing device: _____

Signature: _____ Cadre (e.g. physician, nurse): _____

Full name and surname of assistant: _____

Signature: _____ Cadre (e.g. physician, nurse): _____

Part 3 – Post-Application Evaluation and Assessment (Before Discharge)

Dressing intact and holding penis against abdomen (circle one)? Yes No

Client given post-procedure written instructions (circle one)? Yes No

Clinical disposition of client, including AE management: _____

Oral analgesia given (circle one)? Yes No Drug (name, dose, quantity dispensed): _____

Scheduled removal date (dd-mm-yyyy): _____

Discharged by (Full name and surname): _____

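### Device malfunctions are in the primary endpoint, but a failed or converted placement left without a severity grade has no place in the AE rate or on the AE forms

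*Protocol*

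**What the plan says.** **Endpoint.** Evaluation Endpoints (Executive Summary) and Primary Endpoint (Evaluation Design and Methods) both cover events during and after the procedure and all device-related malfunctions. Assessment starts at device placement.

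**Rate.** The section Adverse Event (AE) and Other Device-Related Incident Documentation says: "The evaluation will compile and analyze mild, moderate and severe AE to determine the AE rate". Other device-related events are summarized separately to inform program policy. The Analysis Overview defines the rate as the percentage of clients with at least one AE, and the upper limit "will be based on a two-sided 95% confidence interval".

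**Forms.** Part 2 of the Appendix IX device CRF asks about an AE during placement. Besides the three grades it offers "Severity cannot be classified (if problem with placement or device malfunction", and a note sends such events to the AE form. The AE form in Appendix XVIII tells staff to enter nothing unless the event is moderate or severe, and has boxes for those two grades only. The device events form in the same appendix offers mild, moderate or severe.

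**Who counts.** Sample Size, Data Collection and Analysis Timeline says males are enrolled until 575 is reached, and also: "Data will continue to be collected until the country has performed 575 circumcisions with the ShangRing device". Client Withdrawal Criteria says: "If a client withdraws after consent, but prior to device placement, the client will be replaced until the desired sample size is reached"; such a client's data are left out of the analysis.

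**Failure is foreseen.** Minimum Site Requirements names certain AEs, device malfunction and displacement as reasons for conversion to surgery. Potential Harm and Measures to Mitigate Harm reports from a Ugandan comparison that "four men who chose ShangRing had to receive conventional circumcision when the ShangRing procedure failed", among 508 who chose the device.

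**The concern.** The endpoint and the rule that turns it into a rate do not cover the same events. The gap falls on the events most specific to the device: a ring that malfunctions, or a placement that cannot be completed and ends in surgery. If these are recorded without a grade, the rate describes safety given a workable placement. The ministry has to decide for all men in whom the device would be tried. Early failures also bear on the secondary endpoint on training. The protocol attributes the Ugandan failures to provider inexperience, and a rate that misses such cases would blur the planned comparison of the training and post-training phases.

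**Working it through.** **1. Follow one event through the protocol.** Suppose a ring malfunctions at placement with no notable bleeding, pain or penile injury, and the circumcision is completed surgically on site.

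- *Appendix IX, Part 2:* an AE during placement is ticked, with severity not classifiable. The note says to complete the AE form.
- *Appendix XVIII, AE form:* the event is not moderate or severe, so the opening instruction says to enter nothing.
- *Appendix XVIII, device events form:* Other, During placement and Surgical can be ticked, but the severity field has no unclassified option. Malfunction and failed placement are not listed event types.
- *Appendix XIX:* the placement-or-wearing block covers anesthetic problems, bleeding, pain and penile injury. Displacement, listed under the removal block, covers a device that has moved or been removed by the client. The residual Other category starts at moderate and requires at least 4 days of disability; severe requires at least 8 days, hospitalization or transfer. None of these need apply here.
- *AE documentation section:* the rate uses three grades. The event has none, so it goes to the separate summary.

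By the endpoint definition this event counts. By the rate rule and the forms it does not.

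**2. Events that do not fall through.** Appendix XIX grades as severe any bleeding at placement that needs device removal or sutures, displacement that needs surgery, and penile injury that needs surgical repair. Conversions for these reasons are in the rate. The gap is the remainder.

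**3. The plan's own figure.** The sample size section says "A minimum of 335 males are necessary for 95% confidence that the population proportion is within" 1.5 percentage points at an observed rate of 2%.

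- n = 1.96² × 0.02 × 0.98 / 0.015² = 334.6, rounded up to 335. This reproduces.
- 335 + 240 = 575.
- Half-width at 575: 1.96 × √(0.02 × 0.98 / 575) = 1.14 points.

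**4. Size of the gap.** The only failure frequency in the protocol is 4/508 = 0.79% (exact 95% CI 0.21% to 2.00%). Applied to 575 this gives 0.0079 × 575 ≈ 4.5, taken as 5. Assume 12 other clients with an AE (2% × 575 = 11.5, rounded), none of them converted, and the converted men added on top of 575. Intervals are exact two-sided 95%.

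| Ungraded conversions | Left out | Counted |
|---|---|---|
| 2 | 12/575 = 2.09% (1.08 to 3.62) | 14/577 = 2.43% (1.33 to 4.04) |
| 5 | 12/575 = 2.09% (1.08 to 3.62) | 17/580 = 2.93% (1.72 to 4.65) |
| 10 | 12/575 = 2.09% (1.08 to 3.62) | 22/585 = 3.76% (2.37 to 5.64) |

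With five conversions the shift is 2.93 − 2.09 = 0.84 points, against the half-width of 1.14. The denominator matters little: 12/580 = 2.07%, and 17/575 = 2.96%. What counts is whether the event enters the numerator.

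**The case against.** A reader might infer something stronger: that converted men are excluded from both the 575 and the AE numerator. The documents do not support that. The sentence on 575 circumcisions sets when data collection ends and defines no analysis set, and the same section counts enrolled males. The replacement rule concerns a client's own withdrawal before placement, not a provider's failed attempt. Two of the three named reasons for conversion, AEs such as bleeding and displacement needing surgery, are already graded severe.

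Capture is also better than a reading of one form suggests. Appendix IX asks whether the device was applied according to its instructions and requires an explanation if not. It is attached to the national client form, which records the surgical method. The AE documentation section requires a form for events whose severity cannot be classified, and has a physician from another site assess each AE, so the clinician's tick is not the final grade. The general definition of moderate (needs intervention, usually managed on site) could be applied to an on-site conversion.

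All of this stands, and it limits how many events would be lost. It does not close the gap. The CRF prints the general definitions and still offers the unclassified box specifically for placement problems and malfunctions. The body text requires a form for these events that, as drafted, refuses them. Nothing says that the outside physician must assign one of the three grades.

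An analysis plan that is not shown may define the analysis set. It cannot supply a conversion outcome that no structured item records, and the conflict between endpoint and rate rule lies within the protocol.

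On size, the four Ugandan failures came early in that evaluation and were put down to inexperience. Here at least 10 supervised placements and certification come before the implementation phase, so 0.8% may be too high for that phase.

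**Conclusion.** The point holds in a limited form. The protocol states an endpoint that includes all device-related malfunctions, then gives a rate rule and forms that leave no place for a malfunction or failed placement without a grade. A failed or converted placement that is not also graded as bleeding, displacement or another listed AE can be left out of the primary rate. Whether such a man counts toward 575 is worded inconsistently; that is an ambiguity and not an exclusion.

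The shift from 2.1% to 2.9% is an upper illustration. It rests on 12 other AE clients, on the cited 4/508 carrying over to these sites, and on no conversion being otherwise graded. The protocol fixes no conversion count, and the true effect could be close to zero if most conversions are graded or if providers are well trained.

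**What to change.** 1. State that the AE analysis set is every client in whom ShangRing placement was started, with no replacement after that point, and use this one definition wherever 575 is mentioned.
2. State that device malfunction or failure to complete placement counts in the primary endpoint even when severity is unclassified, and report it on a separate line as well. The separate line keeps the graded AE rate usable for the planned descriptive comparison with published rates.
3. Add a severity-not-classified option to the AE form and the device events form in Appendix XVIII, and change the AE form's opening instruction to match.
4. Add one item to Appendix IX, Part 2: *Placement completed with ShangRing: yes / no, converted to surgery – reason*.

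The cost is a few sentences, one CRF item and small changes to two forms, with no extra clients or visits. The downside is that the reported rate may be slightly less favourable.
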